10.3.4 Haematology test

Blood samples for haematology test will be withdrawn before treatment initiation on Day 1 of the study (Visit 1, screening procedures), before dosing on Day 4(8) of the study (Visit 2, switch to oral therapy), within 1-2 days (Visit 3) and within 7-9 days (Visit 4) after the last dose.

To evaluate the selection criteria of the study, the Investigator may use haematology test results obtained at the laboratory of the investigational site within 24 hours of study enrollment (Signing of the Informed Consent Form) if he / she considers that available data are sufficient to permit a decision on whether the subject meets the selection criteria. In this case, another blood sampling procedure has to be conducted in the period from the signing of the Informed Consent Form to the start of treatment in order to evaluate all other haematology test parameters that have to be determined on Day 1 in accordance with the study protocol.

Haematology test will be analyzed by the local laboratory of investigational site using standard validated methods. The following investigations will be made:

- erythrocytes
- hemoglobin
- hematocrit
- leucocytes and differential leucocyte count (neutrophils, lymphocytes, monocytes, eosinophils, basophils)
- platelets
- erythrocyte sedimentation rate (ESR).

All clinically significant abnormal changes in haematological parameters from the baseline results must be reported as AEs in the eCRF.

10.3.5 Biochemical assay

Blood samples for biochemical assay will be withdrawn before treatment initiation on Day 1 of the study (Visit 1, screening procedures), before dosing on Day 4(8) of the study (Visit 2, switch to oral therapy), within 1-2 days (Visit 3) and within 7-9

CONFIDENTIAL Page 56 of 88

days (Visit 4) after the last dose. At Visits 1, 2, and 3, samples will be collected prior to dosing.

To evaluate the selection criteria of the study, the Investigator may use blood chemistry test results obtained at the laboratory of the investigational site within 24 hours of study enrollment (Signing of the Informed Consent Form) if he / she considers that available data are sufficient to permit a decision on whether the subject meets the selection criteria. In this case, another blood sampling procedure has to be conducted in the period from the signing of the Informed Consent Form to the start of treatment in order to evaluate all other blood chemistry test parameters that have to be determined on Day 1 in accordance with the study protocol.

Biochemical assay will be performed in the local laboratory of investigational site using standard validated methods. The following investigations will be made:

- glucose
- total bilirubin
- alanine aminotransferase (ALT)
- aspartate aminotransferase (AST)
- gamma-glutamyl transpeptidase (GGTP)
- alkaline phosphatase (ALP)
- potassium (K⁺)
- sodium (Na⁺)
- creatinine
- urea.

All clinically significant abnormal changes in biochemical parameters from the baseline results must be reported as AEs in the eCRF.

10.3.6 Urinalysis

Assessments will be performed in the local laboratory before treatment initiation on Day 1 of the study (Visit 1, screening procedures), before dosing on Day 4(8) of the study (Visit 2, switch to oral therapy), within 1-2 days (Visit 3) and within 7-9 days (Visit 4) after the last dose. The following parameters will be assessed:

- color
- clarity
- specific gravity
- urine pH
- protein
- glucose
- ketones
- erythrocytes
- leucocytes
- epithelium
- bacteria
- crystals
- mucus.

To evaluate the selection criteria of the study, the Investigator may use urinalysis results obtained at the laboratory of the investigational site within 24 hours of study

CONFIDENTIAL Page 57 of 88

enrollment (Signing of the Informed Consent Form) if he / she considers that available data are sufficient to permit a decision on whether the subject meets the selection criteria. In this case, another urine sampling procedure has to be conducted in the period from the signing of the Informed Consent Form to the start of treatment in order to evaluate all other urinalysis parameters that have to be determined on Day 1 in accordance with the study protocol.

All clinically significant abnormal changes in urinalysis parameters from the baseline results must be reported as AEs in the eCRF.

10.3.7 Documentation of adverse events

The Investigator will assess and record in the source documentation and the eCRF any non-serious AEs occurring at each visit from the moment of first IMP administration on Day 1 of Visit 1 until the last procedure at Visit 5. SAEs will be evaluated and recorded in the eCRF from the moment of signing of informed consent on Day 1 of Visit 1 until the last procedure at Visit 5.

All AEs/SAEs observed or reported by the patients will be documented regardless of whether it is related to the investigational product (see Section 11.2).

[figure not shown]
10.4 Drug Concentration Measurements for Assessment of Pharmacokinetic Parameters

Blood sample collection for pharmacokinetic (PK) parameters will be withdrawn on Day 1 and 2 of Visit 1 before and after the first infusion only in 40 first patients enrolled in the investigational sites defined by the Sponsor. Blood collection will be performed via venous catheter which will be inserted into peripheral vein in the arm. Infusions of IMPs should be performed via another peripheral vein during all period of blood collection for PK parameters.

The schedule for blood sample collection for the PK is as follows: pre-dose, 0 h, 0.5 h (±3min), 2.5h (±5min), 4h (±5min), 6h (±10min), 12h (±15min), 16h (±15min) and 22.5h (±15min) after the end of first infusion (see Figure 10-1). The last blood sampling for PK (22.5h after the end of the first infusion) should be conducted just prior to the IMP infusion on study Day 2.

Figure 10-1 Schedule for blood sample collection for the PK at Visit 1

Sample Sample collection (after the end of first infusion on

CONFIDENTIAL Page 58 of 88

a - for these time points the protocol allows acceptable sampling time deviations ("sampling time windows"): 0.5 h±3min, 2.5h±5min, 4h±5min, 6h±10min, 12h±15min, 16h±15min and 22.5h±15min.
 b - The last blood sampling for PK should be conducted just prior to the IMP infusion on study Day 2.

After the last blood sample collection catheter can be used for infusions of IMPs. Drug concentration measurements will be performed in the central laboratory (see Contact information). Detailed information about transportation of the samples and other information are provided in the appropriate Manual.

11 ADVERSE EVENTS (AE) AND SERIOUS ADVERSE EVENTS (SAE)

11.1 Definitions

11.1.1 Adverse Event (AE)

Any untoward medical occurrence in a patient or clinical trial subject administered a medicinal product and which does not necessarily have a causal relationship with this treatment.

An AE can therefore be any unfavourable and unintended sign (including an abnormal laboratory finding which are considered to be clinically significant), symptom, or disease temporally associated with the use of a medicinal product, whether or not considered related to the medicinal product.

Any worsening of symptoms of the primary disease (as compared with estimates made during the screening procedures) should also be registered as an AE.

11.1.2 Drug Relationship

The relationship between an AE and study drugs will be judged according the following categories:

- 1- "Certain": the AE occurs in a plausible time relation to the administration of the drug and cannot be explained by a concurrent disease or other drugs or chemicals. The response to withdrawal of the drug (dechallenge) should be clinically plausible. The event must be definitive pharmacologically or phenomenologically, using a satisfactory rechallenge procedure if necessary.
- 2- "Probable": the AE occurs in a reasonable time relation to the administration of the drug, it is unlikely to be attributed to a concurrent disease or other drugs or chemicals and it follows a clinically reasonable response on withdrawal (dechallenge). Rechallenge information (AE reappearance after drug reintroduction) is not required to fulfil this definition.
- 3- "Possible": the AE occurs with a reasonable time relation to the administration of the drug, but it could also be explained by a concurrent disease or other drugs or chemicals. Information on drug withdrawal (dechallenge) may be lacking or unclear.
- 4- "Unassessable": The relationship cannot be judged, because of the information is insufficient or contradictory and cannot be supplemented or verified.

CONFIDENTIAL Page 59 of 88

- 5- "Unlikely": a causal relationship cannot be definitively ruled out, but
 - other drugs, chemicals or underlying disease provide plausible explanations and/or
 - the temporal relation to the administration of the drug makes a causal relation improbable.
- 6- "Not Related": Any of the following are present:
 - existence of a clear alternative explanation, and/or
 - unreasonable temporal relationship between Drug and Event, and/or
 - non-plausibility

11.1.3 Adverse Drug Reactions

Adverse drug reactions (ADRs) are all untoward and unintended responses to an investigational medicinal product **related** to any dose administered.

The definition implies a reasonable possibility of a causal relationship between the event and the Investigational Medicinal Product (IMP). This means that there are facts (evidence) or arguments to suggest a causal relationship.

11.1.4 Seriousness

An AE/ADR is considered **Serious** when:

- results in death:
- is life-threatening;

Note: Life-threatening is considered any AE in which the subject was at risk of death at the time of the event; it does not refer to an event which hypothetically might have caused death if it were more severe.

- requires inpatient hospitalisation or prolongation of existing hospitalisation;
 - results in persistent or significant disability/incapacity;
 - is a congenital anomaly/birth defect in children born to parents who were exposed to the drug;
- is another medically important condition that may jeopardise the patient or may require intervention to prevent one of the outcomes listed above. Any suspected transmission of an infectious agent via a medicinal product is considered serious and should be assessed under the category of medically important events in the absence of other seriousness criteria.

An AE/ADR is considered **Non-serious** when:

it does not fulfil the conditions for the definition of Serious AE/ADR.

11.1.5 Adverse Event (AE) / Adverse Drug Reaction (ADR) severity

The severity level of a Serious or a Non-serious AE or ADR is attributed according the below definitions.

- **Mild**: does not interfere with routine activities; in case of laboratory tests, when there is a mild abnormality.
- **Moderate**: interferes with the routine activities; in case of laboratory tests, when there is a moderate abnormality.
- **Severe**: makes impossible to perform routine activities; in case of laboratory tests, when there is a significant abnormality.

CONFIDENTIAL Page 60 of 88

If the patient experiences changes in severity of an AE, the event should be captured once with the maximum severity recorded.

11.1.6 Adverse Event (AE) / Adverse Drug Reaction (ADR) expectedness

An AE/ADR is considered Unexpected when the nature, severity or outcome of the AE / ADR is not consistent with the information provided the Instructions for Medical Use (for marketed product) or the IB (for investigational product).

11.1.7 Suspected Unexpected Adverse Drug Reaction (SUSAR)

Any serious unexpected adverse event judged by the Investigator or the Sponsor as drug-related qualifies as suspected unexpected serious ADR (SUSAR). SUSARs are subjected to expedited reporting as specified in Section 11.3.2. Reporting duties of the Sponsor.

11.2 Monitoring and Recording of Adverse Events

At each visit during the study period the Investigator will assess and record in the eCRF any subjective or objective:

- AEs occurred after the first IMP administration on Day 1 of Visit 1 and up to the moment of last procedure at Visit 5
- SAEs occurred after the obtainment of the informed consent (after the signing of ICF) on Day 1 of Visit 1 and up to the moment of last procedure at Visit 5.

AEs communicated by the patient or by the patient's relatives or delegates through phone calls, letters or E-mails will also be recorded. In these cases the Investigator will try to obtain medical confirmation and assessment of the occurred AE.

When an AE has occurred the Investigator will record on the respective electronic Case Report Form Adverse Event (eCRF-AE) recording pages any case, Serious and Non-Serious, whether or not thought to be drug-related, observed in or reported by the patient (or relatives/delegates), specifying the judgement on the causal relationship with the study treatment.

Any available information and diagnostic measure (laboratory and instrumental tests, procedures etc.), will be recorded in the eCRF.

The Investigator is expected to follow-up any AEs occurred during the Study until the resolution of the event or permanent outcome has been determined.

11.3 Management of Serious Adverse Events (SAE)

11.3.1 Reporting duties of the Investigator

The Investigator must report any Serious AE (whether or not thought to be related to the investigational drug) sending the SAE form **no later than 24 hours** after knowledge of the event by the following e-mail or by fax number (if e-mail is not available):

24 h SAE reporting

CONFIDENTIAL Page 61 of 88

E-mail: [contact]

[contact] (information should be marked "To the drug safety department")

When relevant, also the eCRF pages concerning medical history, concomitant medication, laboratory test should be filled.

Any further information and supporting documentation that become available (blinded copies of laboratory reports, tests, procedures, autopsy evidence of the cause of death, etc.) will be provided by the Investigator through additional written reports to the CRO and afterwards forwarded to the Sponsor.

The CRO will inform investigators about all suspected unexpected serious adverse reactions.

11.3.2 Reporting duties of the Sponsor

The Sponsor will ensure that all relevant information about any suspected unexpected serious adverse drug reaction (SUSAR), will be expeditiously reported to the competent Authorities, with these deadlines after the first knowledge (the day when the Sponsor receives the notification of the SUSAR):

- fatal and life threatening cases, no later than 7 days;
- other serious cases, no later than 15 days.

The Sponsor will ensure that all relevant information and supporting documentation that subsequently become available, will be also expeditiously reported as follow up information according to the above mentioned deadlines.

The following safety issues will be subjected to expedited management for the identification of possible adequate actions:

• SAEs associated with the trial procedures.

11.4 Management of adverse events not classified as serious

The Investigator will record all the available information on each occurring AE in the source documentation and the eCRF.

11.5 Pregnancy

All pregnancies detected in the course of the study (including pregnancies of sex partners of male study participants) should be registered in an appropriate manner. The investigator must promptly notify CRO project manager or CRA and the Sponsor using a pregnancy notification form.

If any female patient is found to be pregnant during the study, she should be withdrawn.

All reported pregnancies will be followed up to final outcome, using the pregnancy form. The outcome, including any premature termination, must be reported to the Sponsor.

Pregnancy per se is not an AE, except for the cases when the use of IMPs was

CONFIDENTIAL Page 62 of 88

suspected to reduce the effectiveness of birth control pills. Congenital anomalies and birth defects in children are SAEs. Abortions carried out for medical reasons, as well as any serious complications during pregnancy (including spontaneous abortion) should be also reported as SAEs.

12 STATISTICAL METHODS

12.1 Analysis populations

The following populations will be identified for the statistical analyses:

- Randomized Population (RP): All subjects who were screened and randomized
- Intent-to-Treat Population (ITT): All subjects in the RT population who received at least one complete dose of the drug (Nemonoxacin or Tavanic[®])
- Modified Intent-to-Treat (mITT): Subjects in the ITT population who met the minimal disease criteria (inclusion criteria 3 and 4), and was evaluated for clinical efficacy at least once
- Clinically Evaluable (CE): Per-Protocol subjects in the mITT population (i.e. patients without protocol violations and without a clinical response of "Indeterminate" in the mITT population)
- Bacteriological mITT (b-mITT): Subjects in the mITT population whose bacterial culture yielded at least one baseline bacterial isolate
- Bacteriologically Evaluable (BE): patients in the CE population who had at least one baseline bacterial isolate
- Safety Population (SP): All subjects who received at least one complete dose of the study drug (Nemonoxacin or Tavanic®) and underwent at least one safety evaluation would be included in this data population for safety analysis
- Pharmacokinetic population (PK-C): All subjects who were included in PK study and who had at least 1 measured concentration value.

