3 INTRODUCTION

3.1 Background information

The World Health Organization (WHO) estimates that lower respiratory tract infection (LRTI), including pneumonia, is the third most common cause of death worldwide. LRTI caused 3.1 million deaths in 2012 [23].

Pneumonia is an acute illness characterized by symptoms and signs of lower respiratory tract infection, with new radiographic shadowing for which there is no alternative explanation. Community-acquired pneumonia (CAP) is pneumonia acquired outside a hospital or long-term care facility and being diagnosed within 48 hours of hospital admission [14].

Evidence suggests CAP is most commonly caused by bacterial infection [14].

Streptococcus pneumoniae (the most common etiologic agent), nontypeable Haemophilus influenzae, and the atypical organisms (i.e., Mycoplasma pneumoniae, Chlamydia pneumoniae, and Legionella pneumophila) are the most frequently isolated pathogens from patients of any age who require hospitalization for CAP [17] [20].

Increasing resistance to a variety of antimicrobial agents has been documented in *S pneumoniae* and is common in *H influenzae* as well. In addition to penicillin resistance (penicillin-intermediate S. pneumonia - PISP, or penicillin-resistant S. pneumonia - PRSP), isolates of *S pneumoniae* have demonstrated increasing resistance to other classes of antimicrobials, including macrolides, tetracyclines, trimethoprim-sulfamethoxazole (TMP-SMX), and fluoroquinolones [8] [9]. Surveillance studies indicate that the prevalence of drug-resistant *S.pneumoniae* (DRSP) continues to increase worldwide [8].

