7 SELECTION OF STUDY POPULATION

7.1 Inclusion Criteria

Patients will be eligible for inclusion in the study only if all of the following inclusion criteria are applied:

- 1. Written informed consent obtained from the patient.
- 2. Female and male patients aged between 18 and 70 years inclusive.
- 3. Patients with moderate to severe community-acquired pneumonia who need inpatient treatment (correspondence to at least one of the criteria for hospitalization / preferred hospitalization described in the Appendix 1 of this protocol) but do not need ICU treatment (in case of correspondence to at least one «major» or three «minor» criteria for hospitalization in intensive care unit described in Appendix 1 of this protocol, patient should not be enrolled in the study).
- 4. The presence of at least 3 of the following symptoms/signs:
 - Cough
 - Purulent sputum production
 - Tachypnea (respiratory rate > 24 breaths/minute)
 - Chills
 - Fever (rectal/ tympanic temperature $\geq 38.5^{\circ}\text{C}$ or axillary/ oral/ cutaneous temperature $\geq 38.0^{\circ}\text{C}$)
 - WBC count of $\ge 10.0 \text{ x } 10^9/\text{L}$ or $\ge 15\%$ immature neutrophils (bands; regardless of peripheral WBC count).
- 5. Radiological evidence of (a) new infiltrate(s) consistent with bacterial pneumonia at baseline.
- 6. Treatment-naive patients or patients who have received single dose of a short-acting antibacterial drug within 24 hours of enrollment or patients with treatment failure who have received antibiotics (with the exception of quinolones or fluoroquinolones) for less than 72 hours.
- 7. Consent to use contraception during participation in the study (for women childbearing potential and men).

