12.2 Exclusion of Patients from Analysis

The investigator should not implement any deviation, except where necessary to eliminate an immediate hazard to the patient.

Data obtained from patients with protocol violations/deviations will be included into the efficacy analysis of the modified Intent-to-Treat (mITT) and bacteriological mITT (b-mITT) populations and the safety analysis (safety population, SP) (see Section 12.1). Data obtained from patients with protocol violations and major deviation will not be included into the efficacy analysis of the clinically evaluable (CE) and bacteriologically evaluable (BE) populations (see Section 12.1); however, data obtained from patients with minor deviations may be included into the efficacy analysis of the CE and BE population.

CONFIDENTIAL Page 63 of 88

Any protocol deviations should be documented in the eCRF.

A protocol deviation is any change, divergence, or departure from the study design or procedures of a protocol that is under the investigator's control and that has not been approved by the IEC. Protocol deviations do not interfere with or may not influence significantly the trustworthiness of the obtained data and the results of the clinical study. There are major and minor protocol deviations. Major protocol deviations may lead to quality depreciation of the data for the following analysis (e.g., intake of prohibited medication, skipping TOC visit, etc.). Minor protocol deviations may decrease the data quality, but it is possible to include them in the analysis in CE and BE population (e.g., partial performance of some study procedures, etc.).

A protocol violation is a deviation from the IEC approved protocol that may affect the subject's rights, safety, or well-being and/or the completeness, accuracy and reliability of the study data. The protocol deviation should be referred to violation in the following cases:

- enrollment of patients not eligible according to the inclusion/exclusion criteria,
- enrollment of patients after the Sponsor's announcement about the enrollment termination,
- Poor compliance:
 - Patient took IMPs <80% or >120% predefined total dose (any incomplete intravenous infusion regimen will be recorded as missing 1 dose of drug), or
 - The patient took IMPs <7 days
- Patients who received the treatment different from the one they were randomized to,
- Other deviations that might affect the primary outcome assessment.

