APPENDIX 1: CRITERIA FOR HOSPITALIZATION*

Criteria for hospitalization in patients with a confirmed diagnosis of community-acquired pneumonia*

Patients require hospitalization if they comply with **at least one** of the following criteria:

- 1. Physical examination data:
 - Respiratory rate \geq 30 breaths per minute
 - Diastolic blood pressure ≤60 mm Hg
 - Systolic blood pressure <90 mm Hg
 - Heart rate ≥125 beats per minute
 - Temperature < 35.5°C or ≥ 39.9 °C
- 2. Laboratory data and X-ray findings:
 - WBC count of $< 4.0 \times 10^9 / L$ or $> 20.0 \times 10^9 / L$
 - SaO₂ <92% (measured by pulse oximetry)
 - PaO₂ <60 mm Hg and/or PaCO₂ >50 mm Hg while breathing room-air
 - Serum creatinin >176.7 μ mol/l or blood urea nitrogen >7.0 mmol/l (blood urea nitrogen = urea, mmol/l/2.14)
 - Pneumonic infiltration, involving more than one lobe
 - Cavitation in a lung
 - Pleural effusion
 - Rapid progression of focal-infiltrative lesions in the lungs (> 50% increasing of infiltration size within the previous 2 days)
 - Hematocrit <30% or hemoglobin <90 g/l
 - Extrapulmonary site of infection (meningitis, septic arthritis and other)
 - Sepsis or multiple organ failure, manifested as metabolic acidosis (pH <7.35), coagulopathy
- 3. Impossibility of adequate care and fulfillment of all medical prescriptions at home

Criteria for preferred inpatient treatment for patients with a confirmed diagnosis of community-acquired pneumonia*

Preferred in-patient treatment may also be considered in the following cases:

- 1. Older than 60 years of age
- 2. Concomitant diseases (chronic bronchitis, chronic obstructive pulmonary disease, bronchiectasis, malignancies, diabetes mellitus, chronic renal insufficiency, congestive cardiac failure, chronic alcoholism, drug abuse, significant weight deficit, cerebrovascular diseases)
- 3. Treatment failure after starting treatment with antibiotics
- 4. The desire of the patient and/or his/her family.

CONFIDENTIAL Page 74 of 88

Criteria for Intensive Care Unit treatment for patients with a confirmed diagnosis of community-acquired pneumonia**

The patients require hospitalization in an intensive care unit (in that case the patient will not be enrolled in the study) **if one of** the following major criteria is met:

- Severe respiratory insufficiency requiring mechanical ventilation;
- Septic shock requiring the administration of vasopressors;

OR if the patient meets **three** of the following minor criteria at the same time:

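### The mITT definition does not name the baseline infiltrate (inclusion criterion 5), so patients randomised without one can stay in the primary non-inferiority analysis

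*Combined protocol and SAP*

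**What the plan says.** Section 12.1 starts from randomised patients who received at least one complete dose (ITT). It keeps in mITT those who "met the minimal disease criteria (inclusion criteria 3 and 4), and was evaluated for clinical efficacy at least once". In section 7.1, criterion 3 begins "Patients with moderate to severe community-acquired pneumonia who need inpatient treatment" and refers to Appendix 1. Criterion 4 asks for at least three of six symptoms or signs. Criterion 5 is a separate item: "Radiological evidence of (a) new infiltrate(s) consistent with bacterial pneumonia at baseline".

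Section 12.2 counts enrolment of an ineligible patient as a protocol violation. On such patients it says: "Data obtained from patients with protocol violations/deviations will be included into the efficacy analysis of the modified Intent-to-Treat (mITT" set, among others. Violators are left out of CE. Section 12.6.2 places the primary non-inferiority test in mITT. Section 12.6.3 repeats it in CE as a supportive analysis by the same method.

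Section 3.1 describes the disease in these words: "Pneumonia is an acute illness characterized by symptoms and signs of lower respiratory tract infection, with new radiographic shadowing".

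**The concern.** The mITT restriction is meant to hold the primary comparison to patients who have the disease under study. The protocol's own description of pneumonia has a radiographic element, yet the criterion that records it is not one of the minimal disease criteria.

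If some mITT patients have no infiltrate, and the two drugs do equally well in them, those patients add nothing to the contrast and shrink it. In a superiority trial that is conservative. In a non-inferiority trial it works in favour of the claim.

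The test-of-cure rules do not screen such patients out. Section 10.2.1 assigns the category Cured to any Visit 4 film with no manifestation of pneumonia, without reference to baseline. A patient whose film was clear throughout therefore meets the radiological part of clinical success on either drug.

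**Working it through.** **Who is affected.** Take a patient who meets criterion 4, has no new infiltrate on the baseline film, was randomised in error, received a complete dose and was evaluated once.

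- ITT (12.1): in.
- mITT (12.1): criterion 5 is not tested. The patient is in unless someone rules that criterion 3 also fails, and no rule says so.
- 12.2: the ineligible enrolment is a violation, but violators stay in mITT.
- CE (12.1, 12.2): out.

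**The plan's own figures (12.10).** Inputs: 82% success in both arms, margin 15 points, one-sided 5%, power 80%, 80% of randomised patients in mITT.

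- The step 171 × 0.80 = 136.8, about 137 per arm, reproduces.
- The 137 itself does not follow from the inputs: n = (1.645 + 0.842)² × 2 × 0.82 × 0.18 / 0.15² ≈ 81.1, so 82 per arm (84 with the Farrington-Manning variance).
- With 137 per arm: 0.15 × √(137 / 0.2952) - 1.645 ≈ 1.59, a power of about 94%.

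The planned size is thus larger than its stated inputs need. Here that matters only because it leaves room to lose a few patients.

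**Dilution.** Let f be the share of mITT without an infiltrate. The documents give no value, so f is an assumption. Let q be their success rate, equal in both arms. The other patients have a true deficit exactly at the margin, 67% against 82%. Then:

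- observed difference = -15 × (1 - f) points
- comparator rate = (1 - f) × 0.82 + f × q
- nemonoxacin rate = (1 - f) × 0.67 + f × q

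Example with f = 5% and q = 82%:

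- The rates are 67.75% and 82%, a difference of -14.25 points.
- SE = √[(0.6775 × 0.3225 + 0.82 × 0.18) / 137] ≈ 0.0517.
- z = 0.0075 / 0.0517 - 1.645 ≈ -1.50, so the chance of passing is about 6.7%.

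The table gives the exact binomial probability that the Farrington-Manning test passes at one-sided 5% with 137 per arm, for q from 82% to 100%. The last column is Farrington-Manning power at 82% against 82% once these patients are removed.

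| f | mITT patients (of 274) | Observed difference | False non-inferiority risk | Power after removal (n per arm) |
|---|---|---|---|---|
| 0% | 0 | -15.0 | 5.1% | 93.9% (137) |
| 1% | about 3 | -14.85 | 5.4% | 93.6% (135) |
| 2% | about 5 | -14.7 | 5.7% | 93.4% (134) |
| 5% | about 14 | -14.25 | 6.8-6.9% | 92.8% (130) |
| 10% | about 27 | -13.5 | 9.0-9.1% | 91.5% (123) |

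The success rate assumed for the infiltrate-negative patients hardly matters. The share f drives the result.

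**The case against.** The strongest reply is that criterion 3 already does the work. It names community-acquired pneumonia, and Appendix 1 is headed "Criteria for hospitalization in patients with a confirmed diagnosis of community-acquired pneumonia". Section 3.1 describes pneumonia as an illness "with new radiographic shadowing for which there is no alternative explanation". On that reading, a patient judged not to have pneumonia fails criterion 3 and leaves mITT.

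This stands against two stronger readings that a reader might draw:

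- That patients without pneumonia are knowingly kept in mITT. The text does not say so. The gap is the missing explicit radiological confirmation.
- That criterion 3 can be satisfied by "The desire of the patient and/or his/her family" alone. That item helps decide where a confirmed case is treated; it does not establish the disease.

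The reply does not close the gap. The infiltrate is a separate criterion, 12.1 names only 3 and 4, and two analysts could classify the same patient differently.

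A reader might also infer that film grading at test of cure breaks down when there was no infiltrate at baseline. It does not: Cured is defined in absolute terms, and only the other three categories compare with baseline.

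Two further points stand:

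- Exposure is limited to enrolment errors. Criterion 5 is mandatory, imaging is done at screening or within the preceding 72 hours, a radiologist reads it, eligibility is checked before randomisation, and section 15 provides for 100% source data verification.
- CE removes these patients, so a material effect could show as a gap between mITT and CE. This is only partial protection. CE is supportive, and no agreement with mITT is required. CE can also lose early failures, because patients needing another antibiotic are withdrawn (7.3) and fewer than 7 days of study drug is a violation (12.2).

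Finally, 12.9 leaves detail to a statistical analysis plan to be finalised before database close-out. The text reviewed does not show whether that plan settles the matter.

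**Conclusion.** The point holds as a gap in the definition, with low severity. As 12.1 and 12.2 are written, patients randomised without a confirmed infiltrate can remain in the primary analysis, and the expected bias is towards non-inferiority.

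The size rests on three assumptions: the share f, equal response on both drugs in these patients, and a true deficit of exactly 15 points in the rest. At shares of 1-2%, the error rate rises by 0.3 to 0.6 points. At 5% and 10% it rises by about 1.7-1.8 and 3.9-4.0 points. Nothing in the documents supports shares that high, which would mean about 14 or 27 patients enrolled against a mandatory criterion. The larger figures show the range and are not a forecast, so the realistic effect is probably small.

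**What to change.** In 12.1, change the minimal disease criteria for mITT to inclusion criteria 3, 4 and 5. Determine criterion 5 from the baseline radiologist's report, while blinded and before database lock. Add to 12.2 that its general retention of violators in mITT is subject to this definition.

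The film precedes treatment and is already collected, so the change adds no procedure and no selection related to treatment. It costs one line of text and a few patients in mITT. Even if 10% were removed, power at the stated rates would be about 91.5%, above the planned 80%.
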